Visit 2 (Randomisation/Baseline) should be performed within 14 days after Enrolment visit, when laboratory results from Visit 1 are available. in patients that do not have a recent HbA1c value (within 30 days)

donce a patient is randomised at Visit 2, all visits should be scheduled relative to Visit 2.

'An abbreviated informed consent form will be signed at Screening visit. Review of concomitant medications includes over the counter drugs and herbal/nutritional therapies

Specifications of clinical chemistry laboratory parameters are detailed in CSP Section 5.2.1.3. Visits 1 and 8 to 11 have the same parameters; Visits 2, 12, and 13 have the same parameters; and no clinical chemistry is performed at Visits 3 through 7. CrCl and eGFR will be calculated at all visits.

'Serum lipid panel will include LDL-cholesterol, HDL-cholesterol, triglycerides, and total cholesterol.

Hepatitis panel includes hepatitis B viral antibody IgM, Hepatitis B surface antigen, and hepatitis C virus antibody.

Visit windows for the analysis of efficacy and safety variables are described in detail in Section 4.11.2.

The study will be run at approximately 250 sites mainly in Germany and European Union (EU). Approximately 930 patients (310 patients per treatment group) are planned for randomisation to ensure that at least 290 patients per treatment group are evaluable in the Full Analysis Set (assuming 5% exclusion rate from Full Analysis Set). Assuming however that approximately 30% of screened patients will fail the entry criteria, a total of (approximately) 1329 patients will be enrolled.

Sites will be allowed to perform a pre-study screening assessment (at Week -3) prior to enrolment visit to screen for HbA1c criteria. All potentially eligible patients will be enrolled, provide informed consent, undergo screening for all applicable inclusion/exclusion criteria, and submit laboratory samples at Enrolment (Visit 1, 2 weeks prior to randomisation). Patients should be treated with a stable, maximum tolerated dose of metformin monotherapy (≥1500 mg/day) for at least 8 weeks prior to Enrolment, and remain on the same type and dose of metformin therapy for the duration of the study as the background therapy for all treatment arms, as indicated in Section 1.2.2.

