4.9 Safety analysis

All safety analyses will be performed on the Safety Analysis Set. Summaries of safety data will be produced for the double-blind (DB) treatment period (on-treatment) only, while listings will include all events, i.e., listings will include values during the pre-treatment period, during the DB treatment period and during the follow-up period.

A separate page to capture events of hypoglycaemia is contained within the CRF (AZ module HYPOE). Hypoglycaemia (or discontinuation due to hypoglycaemia) will not be reported on an AE CRF page unless the event fulfilled criteria for SAE (in which case a SAE form will be completed). Hypoglycaemia events that are reported as SAEs will be included in all

summaries of AEs or SAEs. Separate summaries will be provided including hypoglycaemia events reported on that special CRF page (see Section 4.9.6).

Analysis of changes from baseline to a specific time point (e.g., laboratory parameters and vital signs) will only include patients from the Safety Analysis set who have data available for both the baseline and the time point under consideration unless otherwise specified.

SAEs and the lab measurements for the liver function tests will be included in the summaries only if they occurred or were measured on or prior to the 30th day after the last blinded drug treatment date. All other safety events (non-severe AEs, hypoglycaemia, etc.) and measurements (safety labs, vital signs etc.) will be included in the summaries only if they occurred or were measured on or prior to the 4th day after the last blinded drug treatment date.

No formal statistical testing will be performed for safety analyses; only descriptive summaries will be provided. A dot plot (showing relative risk) will be produced for the most common adverse events.

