4.9.6 Hypoglycaemia

Hypoglycaemic events occurring after the start of double blind study medication up to and including 4 days after the last double-blind dosing date will be considered as obtained during the double-blind treatment period and included in the summaries described below.

The proportion of patients with hypoglycaemic events and the number of hypoglycaemic events per patient will be summarised by treatment group. Hypoglycaemic events will also be categorised as follows:

• Major hypoglycaemic events: symptomatic events requiring external assistance due to severe impairment in consciousness or behaviour, with a capillary or plasma glucose

value <54 mg/dL (<3.0 mmol/L), and prompt recovery after glucose or glucagon administration

- Hypoglycaemia: Typical symptoms of hypoglycaemia accompanied by blood glucose \leq 70 mg/dL (3.9 mmol/L)
- Other episodes of hypoglycaemia: Symptoms of hypoglycaemia without a blood glucose reading or symptoms of hypoglycaemia accompanied by blood glucose >70 mg/dL (3.9 mmol/L)
- Confirmed hypoglycaemia: Typical symptoms of hypoglycaemia accompanied by blood glucose ≤50 mg/dL (2.8 mmol/L)
- Asymptomatic hypoglycaemia: An event not accompanied by typical hypoglycaemia symptoms but with measured plasma glucose \leq 70 mg/dL (\leq 3.9 mmol/L)

Hypoglycaemic events leading to discontinuation of study medication will be summarised by treatment. A summary of hypoglycaemic events over time by treatment will also be provided.

Summaries will be produced using data obtained prior to rescue medication only then repeated using all data regardless of use of rescue medication for patients in the Safety Analysis Set. A listing of patients will be produced for all hypoglycaemic events.

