4.9.7 Laboratory evaluation

Unless otherwise specified, laboratory data obtained after the start of study medication and up to and including 4 days (or 30 days for liver function laboratory test) after the last dose of the double-blind treatment period, will be considered as obtained during the double-blind treatment period.

Laboratory data (including haematology, clinical chemistry, creatinine and lipids; Appendix III) will be summarised by visit using the analysis windows defined in Table 12. Values and changes from baseline for laboratory data will be summarised by treatment group at each scheduled visit during the double blind treatment period using descriptive statistics (using all available data regardless of use of rescue medication) for patients in Safety Analysis Data Set. Summaries of laboratory data will be produced for the double-blind treatment period, while listings will include values from the follow-up visit.

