4.11.2 Visit Windows

Deviations are to be expected between patients in the actual number of study days from randomisation to when planned visits are carried out. To handle these deviations in tables, figures, listings, and analyses, visit assessments will be slotted according to visit windows. Data will be assigned to the visit windows using study day. For the efficacy and safety data, the data will be listed and summarised by visit as listed in Table 12 below:

Table 12. Visit windows for efficacy and safety data

Visit	Target	Adjusted windows for analyses (Days)			
	Day	HbA1c	Vital Signs, sBP Body Weight, FPG*, urinalysis hypoglycaemic events	Waist circumference, BMI, ECG, complete physical examination**	Laboratory parameters***, Serum lipids
Baseline	1	≤1	≤1	≤1	≤1
Week 2	15	2 - 21	2 - 21		
Week 4	29	22 - 35	22 - 35		
Week 6	43	36 - 49	36 - 49		
Week 8	57	50 - 63	50 - 63		
Week 10	71	64 - 77	64 - 77		
Week 12	85	78 - 126	78 - 126		
Week 24	169	127 - 210	127 - 210		
Week 36	253	211 - 294	211 - 294		
Week 48	337	295 - 348	295 - 348		
Week 52	365	349 - Last dosing date ⁴ + 7	349 - Last dosing date [¥] + 4*	2 – Last dosing date of the DB period + 4	2 – Last dosing date of the DB period + 4
Follow-up Week 55	386	(Last dosing date $^{4} + 7$) – Last visit date	(Last dosing date [‡] + 4*) – Last visit date		(Last dosing date $^{\frac{1}{4}} + 4$) – Last visit date

^{*:} For FPG, week 52 and week 55 windows use last dosing date +1.

^{**:} also assessed at Week 24; **: clinical chemistry parameters also assessed at Weeks 12, 24, 36, 48.

[¥]: Last dosing date ≥ Day 349

In case of multiple observations within a single visit window, the following rules apply:

- If there are two or more observations within the same visit window, the non-missing observation closest to the target day will be used in the analysis
- If two observations are equidistant from the target day, the non-missing observation with the later collection date will be used in the analysis
- If two observations are collected on the same day and have a collection time associated with them, the non-missing observation with the later collection time will be used in the analysis
- If two or more observations are collected on the same day, all non-missing but with no collection time associated with at least one of them, the average of the observations will be used in the analysis.

If a visit window does not contain any observations, the data will be missing for that visit.

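### Table 12's visit windows conflict with the sections that use them: Week 2–10 creatinine has no row, early stoppers' laboratory values are labelled Week 52, and hypoglycaemic events are not exempted from a one-observation rule

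*SAP*

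**What the plan says.** **The rule.** SAP section 4.11.2 assigns efficacy and safety data to the Table 12 windows by study day. Where a window holds several values, "If there are two or more observations within the same visit window, the non-missing observation closest to the target day will be used". Ties go to the later value. Same-day values are averaged if at least one has no collection time. No variable is exempted, and no rule keeps the worst value.

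**Laboratory data.** The study plan (section 1.2, Table 1) marks creatinine at every visit from enrolment to follow-up, and its footnote says "CrCl and eGFR will be calculated at all visits". Section 4.9.7 names creatinine among the laboratory data that "will be summarised by visit using the analysis windows defined in" Table 12, with values and changes from baseline at each scheduled double-blind visit. The laboratory column of Table 12 has a baseline window, a follow-up window and one on-treatment window, "2 – Last dosing date of the DB period + 4", on the Week 52 row. Its cells for Weeks 2 to 48 are blank. The footnote adds Weeks 12, 24, 36 and 48 for clinical chemistry, without day ranges.

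**Hypoglycaemia.** Table 12 has a column headed "Vital Signs, sBP Body Weight, FPG*, urinalysis hypoglycaemic events", with ten on-treatment windows. Section 4.9.6 states: "A summary of hypoglycaemic events over time by treatment will also be provided" (planned Tables 93 and 94). The same section includes in its summaries all events from the start of study drug to 4 days after the last dose, and asks for the number of events per patient.

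**The concern.** A closest-to-target rule suits a repeated measurement such as weight. It does not suit events, where every occurrence counts and the most severe one matters most. If a programmer follows Table 12 for Tables 93–94, repeat events disappear and a major event can give way to a milder one nearer the target day. The loss grows with the event rate, so the arm with more repeat events would be undercounted more and the difference between arms by period would shrink.

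For creatinine, a table that section 4.9.7 requires cannot be built from the windows it cites. Renal impairment/failure and volume depletion are adverse events of special interest (section 4.9.4), so the early course of creatinine and eGFR is of interest. The Week 52 row would also mix true Week 52 values with values from patients who stopped months earlier, without saying so.

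**Working it through.** The SAP states no figure to reproduce, so the check applies its rules to its own visit days.

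**Creatinine**

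1. Scheduled on-treatment target days (Table 12): 15, 29, 43, 57, 71, 85, 169, 253, 337 and 365, ten in all.
2. Printed laboratory window: Day 2 to last dose + 4. With a last dose on Day 365 this is Days 2–369, and all ten values fall inside it.
3. Completer: the value closest to Day 365 is the Day 365 value. The footnote names Weeks 12–48 for clinical chemistry, so Days 85, 169, 253 and 337 could be given rows with day ranges borrowed from another column. Days 15, 29, 43, 57 and 71 have neither a range nor a footnote: 5 of 10 values without a row.
4. Patient who stops at Week 10: the available values are Days 15 to 71. The closest to Day 365 is Day 71, which is reported as Week 52.
5. Comparison: section 4.9.9 openly states a last-observation rule for ECG. Sections 4.9.7 and 4.11.2 state none for laboratory data.

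**Hypoglycaemia, one hypothetical patient**

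The Week 24 window is Days 127–210, target Day 169. Suppose a major event on Day 130, an other episode on Day 168 and an event with glucose ≤70 mg/dL on Day 200. The distances to target are 39, 1 and 31 days. The rule keeps Day 168 and drops two of the three events, including the major one.

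**Hypoglycaemia, illustrative share lost**

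- Window widths in days: 20, 14, 14, 14, 14, 49, 84, 84 and 54 for Weeks 2–48, and 21 for Week 52 (Days 349–369, assuming a last dose on Day 365). The sum is 368.
- Assumption: events follow a Poisson process at a constant rate r per patient-year. The SAP gives no rate.
- Expected events in a window of width w: λ = r × w/365. Expected events kept: 1 − exp(−λ). Share lost: 1 − Σ(1 − exp(−λ))/Σλ.

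| r per patient-year | Expected events | Events kept | Share lost |
|---|---|---|---|
| 1 | 1.01 | 0.93 | 7% |
| 3 | 3.02 | 2.43 | 20% |
| 6 | 6.05 | 4.03 | 33% |
| 12 | 12.10 | 5.96 | 51% |

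For r = 12: one 20-day window keeps 0.482, four 14-day windows 4 × 0.369, one 49-day window 0.800, two 84-day windows 2 × 0.937, one 54-day window 0.831 and one 21-day window 0.499. These sum to 5.96, and 1 − 5.96/12.10 = 0.51.

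The number of patients with at least one event in a window is unchanged, because the rule always keeps one event.

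**The case against.** **Hypoglycaemia.** Section 4.11.2 opens by speaking of visit assessments, and its tie rules refer to collection dates and times, which is the language of measurements. Listing events in a column may mean only that they are allocated to periods. Section 4.9.6 is the more specific text and includes all on-treatment events. The SAP shows no layout for Tables 93–94; if they report only patients with any event, nothing is lost. This stands to the extent that an undercount is not certain. A reader might infer that these tables will understate events, or that the hypoglycaemia endpoint is biased. The documents support neither: the first depends on which section the programmer follows, and the key secondary proportion and Tables 91–92 do not use the windows. What remains is that events are named in the table and the SAP does not say which section governs.

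**Creatinine.** Section 4.9.7 requires a summary at each scheduled visit, so blank cells cannot mean that none is intended. Weeks 12–48 are equally blank, yet the footnote names them. A wide final window also fits a design in which early terminators complete the end-of-treatment procedures, and haematology and lipids have no other scheduled on-treatment sample. These points explain the layout but supply no day ranges. A reader might also infer that early renal changes are lost altogether. They are not: marked abnormalities (section 4.9.7.1, Table 15) are judged on on-treatment values, renal adverse events are tabulated, and the laboratory listings remain.

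**Section 4.9.** It limits change-from-baseline summaries to patients "who have data available for both the baseline and the time point under consideration". It is tempting to call the Week 52 window a breach of this, but the sentence goes on to allow exceptions, and Table 12 can be read as one. The fair criticism is that the carried-forward value is not labelled.

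**Conclusion.** The point holds as a conflict between Table 12 and the sections that rely on it, confined to descriptive by-visit safety tables. The creatinine part is the firmer: the required by-visit summary has no printed windows for Weeks 2–48, five of ten scheduled values have neither a range nor a footnote, and an early stopper's value would be labelled Week 52. The hypoglycaemia part is conditional: if the one-observation rule is applied to Tables 93–94, event counts and severity by period are understated. The 7% to 51% range illustrates this for assumed constant rates of 1 to 12 events per patient-year and is not a prediction for this trial. Safety data are not formally tested (section 4.9), and no primary or key secondary result changes. The plan should still be corrected, because its rules followed literally give wrong tables.

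**What to change.** 1. In section 4.11.2, state that for hypoglycaemic events the windows only allocate events to periods. All events are counted, and the worst category is shown per patient and period. Cross-refer to section 4.9.6.
2. In Table 12, give creatinine, CrCl and eGFR the Week 2–48 day ranges already used for vital signs (2–21, 22–35, 36–49, 50–63, 64–77, 78–126, 127–210, 211–294, 295–348), with Week 52 starting at Day 349.
3. Give clinical chemistry the same ranges for Weeks 12–48, again with Week 52 starting at Day 349.
4. Where the window from Day 2 to last dose + 4 is kept (haematology, lipids), label the result 'last on-treatment value' instead of Week 52.

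The cost is a text edit to Table 12 and its rules, and extra rows in tables already planned. No new data are needed.

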4.11.3 Post-Dosing Observations

While double blind treatment period efficacy and safety observations will be listed regardless of whether the patient was taking blinded study drug, observations will be summarised only when the following rules are satisfied:

For efficacy parameters

- HbA1C, body weight, BMI and waist circumference will be summarised only if measured on or before the 8th day after the last double-blind drug dosing date.
- FPG, will be summarised only if measured on or before the first day after the last randomised, double-blind drug dose date.
- SBP will be summarised only if measured on or before the 4th day after the last double-blind drug dosing date.

For safety parameters

- SAEs and the lab measurements for the liver function tests will be included in the summaries only if occurred/measured on or prior to the 30th day after the last blinded drug treatment date.
- All other safety events (non-severe AEs, hypoglycaemia, etc.) and measurements (safety lab, vital signs, etc.) will be included in the summaries only if occurred/measured on or prior to the 4th day after the last blinded drug treatment date.

4.11.4 Duration of Type 2 Diabetes and Missing Dates

Duration of Type 2 diabetes is calculated as the number of years from Type 2 diabetes diagnosis date to informed consent date:

(1 + consent date - diagnosis date) / 365.25

If the date Type 2 diabetes was diagnosed is partially missing, the following rules will take effect:

- Missing day, but month and year are present: the day will be imputed as the 15th day of the month.
- Missing day and month, but year is present: the day and month will be imputed as 30 June of the year (provided that the imputed date is less than the consent date).
- Missing year, but day and month are present: No imputations will occur, and the patient will be excluded from all summaries related to duration of Type 2 diabetes.
- Missing day, month and year: No imputations will occur, and the patient will be excluded from all summaries related to duration of Type 2 diabetes
- If any such imputed date falls after the consent date, then the diagnosis date will be taken as equal to the consent date.

These durations, even if partially imputed, will be listed. However, only the portion of the date of diagnosis actually observed, rather than imputed dates, will be displayed in listings.

4.11.5 Missing Dates for Adverse Events

If missing or partial dates of AE onset occur, a conservative approach will be followed and events will be assumed to be during the Double-Blind treatment period unless there is convincing evidence to the contrary. For AEs, a missing or incomplete onset date will be imputed according to the following conventions:

- If the onset date for an AE is missing or incomplete, an imputed date will be derived to slot the event to an appropriate analysis period (pre-treatment, during DB treatment or follow-up). This derived date will not be reported in summary tables or listings. Every effort will be made to determine the actual onset date for the event or to obtain a reliable estimate for the onset date from the investigator.
- If an onset date is missing, the derived onset date will be calculated as the first non-missing valid date from the following list (in order of precedence):
 - o First active study medication date
 - Visit date corresponding to the visit at which the event was reported.
 - o If a valid non-missing date is not available for any of these dates, the derived onset date will be set to missing.
- If an onset date is incomplete, the derived onset date will be calculated using the following algorithm:
 - Calculate a surrogate date as the first non-missing valid date from the following list (in order of precedence):
 - First active study medication date
 - Visit date corresponding to the visit at which the event was reported
 - If a valid non-missing date is not available for any of these dates, the surrogate date will be set to missing.

- o Based on the information provided, set the derived date to the earliest possible date. If only a year is provided, set the derived date to January first of that year. If a year and month is provided, set the derived date to the first day of that month.
- o If the surrogate date is non-missing then:
 - If the derived date is on or after the surrogate date use the derived date as calculated
 - If the derived date is before the surrogate date and the surrogate date is consistent with the partial data provided for the onset date, use the surrogate date as the derived date
 - If the derived date is before the surrogate date and the surrogate date is not consistent with the partial data provided for the onset date then set the derived onset date to be the latest possible date based on the partial onset date information provided. If only a year is provided, set the derived date to December 31st of that year. If a year and month is provided, set the derived date to the last day of that month.
- o If all three dates used to determine the surrogate date are missing, then based on the information provided, set the derived date to the earliest possible date. If only a year is provided, set the derived date to January first of that year. If a year and month is provided, set the derived date to the first day of that month.

4.11.6 Counting Rules for Adverse Events

Where a patient has the same AE, based on preferred terminology, reported multiple times in a single analysis period, the patient will only be counted once at the preferred terminology level in AE frequency tables.

Where a patient has multiple adverse events within the same system organ class in a single analysis period, the patient will only be counted once at the system organ class level in adverse event frequency tables.

When a patient has the same AE, based on preferred terminology, reported multiple times in a single analysis period, the following criteria, in order of precedence, will be used to select the event to be included in summary tables:

- **Relationship to study medication**: Related events will take precedence over unrelated events in determining the event to include in summary tables.
- **Intensity of event:** More intense events will take precedence over less intense events in determining the event to include in summary tables. Missing intensity will be considered the least intense event.
- **Onset date:** Earlier onset date events will take precedence over later onset date-time events in determining the event to include in summary.

When reporting AEs by intensity, in addition to providing a summary table based on the event selection criteria detailed above, summary tables will also be provided based on the most

intense event during the analysis period - independent of relationship to study medication. For these tables, the following criteria, in order of precedence, will be used to select the event to be included in summary tables:

- Intensity of event
- Onset date

